# 4. Study Design

## 4.1. Overall Design

This is an exploratory study in healthy adult participants aged 18-55 years. The study is formed of two parts, Part 1 and Part 2.

#### 4.1.1. Part 1 design

All participants in Part 1 will receive the following on Day 0:

#### • Reference article product

Palivizumab (Synagis™) Dose: 8mg/Kg

If there are no safety concerns in Part 1, and PK analysis of Palivizumab treated participants confirm dose level 8mg/Kg to be appropriate, Part 2 will commence with the planned 8mg/Kg treatment dose. However, if PK analysis of Part 1 suggests that 8mg/kg may be insufficient dose to provide suitable efficacious coverage in Part 2, then Part 2 will proceed with a dose of 15mg/Kg.

#### 4.1.2. Part 2 design

Participants in Part 2 will be pre-screened for susceptibility to RSV infection, i.e., have levels of RSV neutralising antibodies compatible with susceptibility to RSV infection (the cut-off is based on the average 25th percentile of the past 12 months screening results).

Participants in Part 2 will be randomised to receive the following on Day -1:

#### Reference article product

- Palivizumab (Synagis™)
- Dose: either 8mg/Kg or 15mg/Kg (as determined from Part 1)

#### Placebo product

o Sodium Chloride 0.9% Solution (Normal Saline) matched to reference article product

All participants in Part 2 will subsequently receive the following on Day 0:

## RSV challenge virus

 RSV-A Memphis 37b, total dose of approximately 4.5 log10 plaque forming unit, given intranasally

The Study Schematic - showing participant progression through the study - is presented in Section 1.2; the Schedules of Activities (SoA) are presented in Section 1.3.

#### 4.1.3. Part 1 duration

The total duration of study participation for a participant is up to approximately 52 days, with the following sequence and duration of study periods:

- Screening phase: from Day -28 to Day -1 pre-admission (Historical generic screening data collected through the hVIVO Generic Screening process may be transferred to this study after the study-specific consent form has been signed by the participant).
- **Inpatient phase:** Participants will be resident in the Unit for 1 days (from Day 0 to Day +1). Procedures will include:
  - Admission to Unit on Day 0
  - Study intervention I.V. dosing on Day 0
  - o Post infusion monitoring and PK Day 0 and Day1
  - Participants will be discharged from the Unit on Day 1 (or may remain longer at the Principal Investigator's discretion)
- Outpatient phase: study assessments will be conducted at follow up clinic visits and telephone calls as follows:
  - Clinic visits: Day 2, Day 3, Day 7 (±1 day) and Day 12
  - o Final safety follow-up by telephone: Day 18 (±3 days).

#### 4.1.4. Part 2 duration

The total duration of study participation for a participant is up to approximately 122 days, with the following sequence and duration of study periods:

- **Screening** phase: from Day -90 to Day -4 pre-quarantine admission (Historical generic screening data collected through the hVIVO Generic Screening process may be transferred to this study after the study-specific consent form has been signed by the participant).
- **Inpatient phase:** Participants will be resident in the Quarantine Unit for approximately 16 days (from Day -3 to Day +12). Procedures will include:
  - o Pre-HVC:
- Admission to Quarantine Unit on Day -3
- Study intervention I.V. dosing on Day -1
- o HVC:
- Challenge Virus inoculation on Day 0 (window 1 to 2 days post-treatment)
- Post-HVC
- Day 0 onwards and each day study assessments will be conducted as per Schedule of Activities
- Participants will be discharged from the Quarantine Unit on Day12 (or may remain longer at the Principal Investigator's discretion)
- Outpatient phase: study assessments will be conducted
  - Clinic visit for PK sample on Day 20 (±2 days)
  - Final safety follow-up visit(s): Day 28 (±3 days)

The study will be conducted by hVIVO which has extensive experience with RSV challenge studies. Numerous studies have been performed using experimental RSV infection in human participants. To date, in hVIVO's studies, over 1220 healthy participants (18 to 55 years of age) have been successfully and safely inoculated with RSV-A Memphis 37b. These studies demonstrated that adults could be infected by nasal inoculation and that experimental infection was safe. This strain has been shown to cause symptoms and virus shedding that closely match natural infection.

Administration of study intervention and challenge with RSV-A Memphis 37b will take place in hVIVO's specialised Clinical Units, either in the Quarantine Unit or Screening Clinic Units. Standard study procedures (including collection of blood, urine, and nasopharyngeal secretions for assessment of safety and efficacy) have been employed in previous studies conducted by hVIVO.

#### 4.2. Scientific Rationale for Study Design

This RSV Memphis 37b strain has been shown to cause symptoms and virus shedding that closely match natural infection in otherwise healthy adults.

Administration of study intervention and challenge with RSV-A Memphis 37b will take place in hVIVO's specialised Clinical Units, either in the Quarantine Unit or Screening Clinic Units. Standard study procedures (including collection of blood, urine, and nasopharyngeal secretions for assessment of safety and efficacy) have been employed in previous studies conducted by hVIVO.

#### 4.3. Justification for Treatment Dose & Route of Administration

The dose regimen of 8mg/kg in part 1 and 8mg/kg or 15mg/kg Palivizumab in part 2 of the study is supported by data from previous clinical trials and human experience referenced in this protocol, SmPC and the accompanied document "PALIVIZUMAB Summary of relevant clinical and non-clinical data to support the use of IMP in the clinical trial".

Studies performed in adult volunteers showed that the half-life of elimination of the drug was approximately 17-20 days when administered either IV or IM and was safe through at least three-monthly injections (with the upper most test dose of 15 mg/kg). There were no safety signals in the adult volunteer studies. A single IV dose in adult volunteers at twice the recommended palivizumab prophylaxis dose has been shown to be well tolerated.

Details of clinical studies to examine the comparability of the human safety, tolerability, immunogenicity and pharmacokinetics characteristics of the liquid and the lyophilized preparations of Synagis are listed in accompanied document "PALIVIZUMAB Summary of relevant clinical and non-clinical data to support the use of IMP in the clinical trial".

## 4.4. End of Study Definition

A participant is considered to have completed the study if he/she has completed all phases of the study including the last scheduled procedure shown in the SoA relevant for each part of the study or the last unscheduled visit as applicable. If a safety visit is required after the last scheduled visit, this will be at the PI's discretion as a duty of care, e.g., repeat spirometry or laboratory tests. These discretionary follow-up visits will not be considered part of the trial data unless they represent follow-up and closure on an AE or serious adverse event (SAE) identified during the trial period.

The end of the study is defined as the date of the last visit of the last participant in the study.

# 5. Study Population

Prospective approval of protocol deviations to recruitment and enrolment criteria, also known as protocol waivers or exemptions, is not permitted.

# 5.1. Inclusion Criteria

Participants are eligible to be included in the study only if all of the following criteria apply:

NO	INCLUSION CRITERIA			
1	An informed consent document signed and dated by the participant and the Investigator.			
2	Aged between 18 and 55 years old on the day of signing the consent form.			
3	In good health with no history, or current evidence, of clinically significant medical conditions, and no clinically significant test abnormalities that will interfere with participant safety, as defined by medical history, physical examination, (including vital signs), Electrocardiogram (ECG), and routine laboratory tests as determined by the Investigator.			
4	A documented medical history prior to enrolment.			
5	The following criteria are applicable to female participants participating in the study.  a) Females of childbearing potential must have a negative pregnancy test prior to enrolment.  b) Females of non-childbearing potential:  a. Post-menopausal females; defined as having a history of amenorrhea for >12 months with no alternative medical cause, and /or by FSH level >40mIU/mL, confirmed by laboratory.  b. Documented status as being surgically sterile (e.g. tubal ligation, hysterectomy, bilateral salpingectomy and bilateral oophorectomy).			
6	The following criteria apply to female and male participants:  a) Female participants of childbearing potential must use one form of highly effective contraception. Hormonal methods must be in place from at least 2 weeks prior to the first study visit. The contraception use must continue until 30 days after the date of viral challenge/last dosing with IMP (whichever occurs last). Highly effective contraception is as described below:  a. Established use of hormonal methods of contraception described below (for a minimum of 2 weeks prior to the first study visit). When hormonal methods of contraception are used, male partners are required to use a condom with a spermicide:			

- i. combined (oestrogen and progestogen containing) hormonal contraception associated with inhibition of ovulation:
  - 1. oral
  - 2. intravaginal
  - 3. transdermal
- ii. progestogen-only hormonal contraception associated with inhibition of ovulation:
  - 1. oral
  - 2. injectable
  - 3. implantable
- b. Intrauterine device (IUD)
- c. Intrauterine hormone-releasing system (IUS)
- d. Bilateral tubal ligation
- e. Male sterilisation (with the appropriate post vasectomy documentation of the absence of sperm in the ejaculate) where the vasectomised male is the sole partner for that woman.
- f. True abstinence sexual abstinence is considered a highly effective method only if defined as refraining from heterosexual intercourse during the entire period of risk associated with the study treatments. The reliability of sexual abstinence needs to be evaluated in relation to the duration of the clinical trial and the preferred and usual lifestyle of the participant.
- b) Male participants must agree to the contraceptive requirements below at entry to quarantine and continuing until 90 days after the date of Viral challenge / last dosing with the investigational medicinal product (IMP) (whichever occurs last):
  - a. Use a condom with a spermicide to prevent pregnancy in a female partner or to prevent exposure of any partner (male and female) to the IMP.
  - b. Male sterilisation with the appropriate post vasectomy documentation of the absence of sperm in the ejaculate (please note that the use of condom with spermicide will still be required to prevent partner exposure). This applies only to males participating in the study.
  - c. In addition, for female partners of child bearing potential, that partner must use another form of contraception such as one of the highly effective methods mentioned above for female participants.
  - d. True abstinence sexual abstinence is considered a highly effective method only if defined as refraining from heterosexual intercourse during the entire period of risk associated with the study treatments. The reliability of sexual abstinence needs to be evaluated in relation to the duration of the clinical trial and the preferred and usual lifestyle of the participant.
- c) In addition to the contraceptive requirements above, male participants must agree not to donate sperm following discharge from quarantine until 90 days after the date of Viral Challenge/last dosing with IMP (whichever occurs last).

For Part 2 of the study:

Sero-suitable to the challenge virus, as defined in the study Analytical Plan.

# 5.2. Exclusion Criteria

Participants are excluded from the study if any of the following criteria apply:

NO	STANDARD EXCLUSION CRITERIA				
Medical H	istory				
1	History of, or currently active, symptoms or signs suggestive of upper or lower respiratory tract infection within 4 weeks prior to the first study visit.				
	
 
a) Any history or evidence of any other clinically significant or currently active systemic comorbidities including psychiatric disorders (includes participants with a history of depression and/or anxiety).
 
b) And/or other major disease that, in the opinion of the Investigator, may put the participant at undue risk, or interfere with a participant completing the study and necessary investigations.
 
				
2	
 
Participants with clinically mild atopic eczema/atopic dermatitis and clinically mild psoriasis may be included at the Investigator's discretion (e.g., if small amounts of regular topical steroids are used, no eczema in cubital fossa; moderate to large amounts of daily dermal corticosteroids is an exclusion).
 
Rhinitis (including hay fever) which is clinically active or history of moderate to severe rhinitis, or history of seasonal allergic rhinitis likely to be active at the time of inclusion into the study and/or requiring regular nasal corticosteroids on an at least weekly basis, within 30 days of admission to quarantine will be excluded. Participants with a history of currently inactive rhinitis (within the last 30 days) or mild rhinitis may be included at the Pl's discretion.
 
Participants with a physician diagnosed underactive thyroid who have been controlled on treatment for at least 6 months with evidence of a normal thyroid function test (TFT) can be included at the discretion of the Pl.
 
Any concurrent serious illness including history of malignancy that may interfere with the aims of the study or a participant completing the study. Basal cell carcinoma within 5 years of initial diagnosis or with evidence of recurrence is also an exclusion.
 
Participants with a history of psychiatric illness including depression and/or anxiety of any severity within the last 2 years can be included if the Patient Health Questionnaire (PHQ-9) and / or the Generalised Anxiety Disorder Questionnaire
 
				

NO	STANDARD EXCLUSION CRITERIA
	
 
between 5 and 9 may be included following consultation with a Senior Physician (Clinical Lead for Screening) who may advise further consultation with the PI.
 
Participants reporting physician diagnosed migraine can be included provided there are no associated neurological symptoms such as hemiplegia or visual loss. Cluster headache/migraine or prophylactic treatment for migraine is an exclusion.
 
Participants with physician diagnosed mild Irritable Bowel Syndrome (IBS) not requiring regular treatment can be included at the discretion of the PI.
 

3	Participants who have smoked ≥ 10 pack years at any time [10 pack years is equivalent to one pack of 20 cigarettes a day for 10 years]).
4	A total body weight ≤ 50 kg and Body Mass Index (BMI) ≤18 kg/m2 and ≥30kg/m².
5	Females who:  a) Are breastfeeding, or  b) Have been pregnant within 6 months prior to the study.
6	History of anaphylaxis-and/or a history of severe allergic reaction or significant intolerance to any food or drug, as assessed by the PI.
7	Venous access deemed inadequate for the phlebotomy and cannulation demands of the study.
8	
 
a) For Part 2 of the study: Any significant abnormality altering the anatomy of the nose in a substantial way or nasopharynx that may interfere with the aims of the study and in particular any of the nasal assessments or viral challenge, (historical nasal polyps can be included, but large nasal polyps causing current and significant symptoms and/or requiring regular treatments in the last month will be excluded).
 
b) Any clinically significant history of epistaxis (large nosebleeds) within the last 3 months of the first study visit and/or history of being hospitalized due to epistaxis on any previous occasion.
 
c) Any nasal or sinus surgery within 3 months of the first study visit.
 

Prior or C	oncomitant Medications and Assessments
9	For Part 2 of the study:  a) Evidence of vaccinations within the 4 weeks prior to the planned date of viral challenge/first dosing with IMP (whichever occurs first).  b) Intention to receive any vaccination(s) before the last day of Follow-up. (NB. No travel restrictions will apply after the Day 28 (±3 days) Follow-up Visit).
10	Receipt of blood or blood products, or loss (including blood donations) of 470 mL or more of blood during the 3 months prior to the planned date of viral challenge/first dosing with IMP (whichever occurs first) or planned during the 3 months after the final visit.
11	a) Receipt of any investigational drug within 3 months prior to the planned date of viral challenge/first dosing with IMP (whichever occurs first).

NO	STANDARD EXCLUSION CRITERIA			
	b) Receipt of three or more investigational drugs within the previous 12 months prior to the planned date of viral challenge/first dosing with IMP (whichever occurs first).			
	For Part 2 of the study:			
	
 
c) Prior inoculation with a virus from the same virus-family as the challenge virus.
 
d) Prior participation in another human viral challenge study with a respiratory virus in the preceding 3 months, taken from the date of viral challenge in the previous study to the date of expected viral challenge in this study.
 
			
	
 
a) Confirmed positive test for drugs of abuse on first study visit. One repeat test allowed at PI discretion.
 
			
12	b) History or presence of alcohol addiction, or excessive use of alcohol (weekly intake in excess of 28 units alcohol; 1 unit being a half glass of beer, a small glass of wine or a measure of spirits), or excessive consumption of xanthine containing substances (e.g. daily intake in excess of 5 cups of caffeinated drinks e.g. coffee, tea, cola).			
13	For Part 2 of the study: A forced expiratory volume in 1 second (FEV1) < 80%.			
14	Positive human immunodeficiency virus (HIV), active hepatitis A (HAV), B (HBV), or C (HCV) test.			
Other				
15	Those employed or immediate relatives of those employed at hVIVO or the Sponsor.			
16	Any other finding that, in the opinion of the Investigator, deems the participant unsuitable for the study.			

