## 8.3. Height, Weight and Body Mass Index (BMI)

Height and weight measurements will be recorded in compliance with hVIVO's standard procedures.

BMI will be calculated as: BMI (kg/m2) = Weight (kg)
Height (m)2

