#### 8.19. Blood Samples

A maximum volume of 470 mL of blood may be taken from each participant from screening through to the final study contact. If additional samples are required in excess of this amount, e.g., to monitor abnormalities, these will be collected at the discretion of the Investigator.

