#### 3.3.2.2 Evaluable

All participants randomly assigned to study intervention and who take a dose of study treatment, are given viral challenge, and who complete quarantine. Except those participants with protocol deviations that lead to exclusion.

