#### 3.3.2.5 Protocol deviations

All deviations will be reviewed and adjudicated as either major with potential impact on efficacy evaluation, major deviations without impact on efficacy evaluation or minor deviations during the blind review meeting, before database lock and code break.

Major protocol deviations are defined as deviations liable to either impact the rights, safety or well-being of the patient or to prevent or change the interpretation of the results of the primary efficacy analysis of the study.

The following deviations will be considered as major (this list is not exhaustive and will be reviewed at the time of the blind review meeting):

- non compliance with the inclusion or non inclusion criteria
- non compliance with the randomisation procedure
- non compliance with study treatment
- non compliance with challenge virus inoculation
- no post-baseline data for the primary efficacy endpoint
- intake of forbidden medication

All other deviations will a priori be considered as minor deviations.

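### Exclusion 4 joins its weight and BMI limits with 'and', so as written it excludes nobody, and repairing the BMI pair alone still leaves readings that sort volunteers differently

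*Protocol*

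**What the plan says.** Exclusion 4 in Protocol 5.2 reads in full: "A total body weight ≤ 50 kg and Body Mass Index (BMI) ≤18 kg/m2 and ≥30kg/m²". The sentence above the exclusion list says: "Participants are excluded from the study if any of the following criteria apply". Protocol 8.3 defines BMI as weight divided by height squared and sets no limits. Neither document gives another weight or BMI range for entry.

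Protocol 5 rules out waivers: "Prospective approval of protocol deviations to recruitment and enrolment criteria, also known as protocol waivers or exemptions, is not permitted". In the SAP, section 3.3.2.5 (Part 2) lists among the major deviations "non compliance with the inclusion or non inclusion criteria". SAP 3.3.2.2 defines the Part 2 Evaluable set with the clause "Except those participants with protocol deviations that lead to exclusion". SAP 5.3 bases the efficacy analysis on that set.

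**The concern.** All three parts of the criterion are joined by 'and', and two of them are opposite ends of the BMI scale. Taken at its word, the criterion can never apply. Most readers will repair the BMI pair without noticing. The first 'and' is harder, because low weight together with low BMI is a coherent joint condition. A careful reader could keep that 'and' and change only the second.

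Two things depend on the answer. The first is eligibility. This is the only numeric body-size limit in a trial that doses by weight and states that "A maximum volume of 470 mL of blood may be taken from each participant from screening through to the final study contact". With waivers barred, staff need a rule that can be applied as written. The second is analysis. The blind review must decide whether criterion 4 was breached, and the text gives no single answer for some body sizes.

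**Working it through.** The plan states no figure to reproduce. This is a check of logic, with a little arithmetic on examples.

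**Inputs.** The limits are 50 kg, BMI 18 and BMI 30 (Protocol 5.2, exclusion 4). BMI = weight in kg / (height in m)² (Protocol 8.3). The example heights and weights are chosen here for illustration.

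**Step 1: the literal text.** The condition is weight ≤50 and BMI ≤18 and BMI ≥30. Each person has one BMI at a visit, so the last two parts cannot both hold. Nobody is excluded.

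**Step 2: does the list heading repair it?** No. The phrase about any of the criteria applying joins the numbered criteria to one another. It does not change the connectives inside criterion 4. The same table uses 'or' for alternatives elsewhere (criteria 5, 10 and 12b, for instance), so 'and' is not its usual way of writing 'or'.

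**Step 3: the repaired readings.**

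- A: weight ≤50, or BMI ≤18, or BMI ≥30. Both connectives are changed.
- B: (weight ≤50 and BMI ≤18), or BMI ≥30. Only the second is changed.
- C: weight ≤50, and (BMI ≤18 or BMI ≥30). Only the second is changed, with the BMI pair grouped.

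**Step 4: where A and B differ.** Both exclude BMI ≥30. Below 30, A excludes anyone with low weight or low BMI, while B excludes only those with both. They therefore differ for people with exactly one of the two:

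- weight ≤50 kg with BMI above 18 and below 30;
- BMI ≤18 with weight above 50 kg.

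Under C the upper BMI limit could apply only up to a height of √(50/30) = 1.29 m, so C is a poor candidate for the intended meaning.

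**Step 5: examples.**

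| Weight, height | BMI | Literal | A | B | C |
|---|---|---|---|---|---|
| 48 kg, 1.55 m | 48/1.55² = 20.0 | eligible | excluded | eligible | eligible |
| 56 kg, 1.80 m | 56/1.80² = 17.3 | eligible | excluded | eligible | eligible |
| 95 kg, 1.75 m | 95/1.75² = 31.0 | eligible | excluded | excluded | eligible |
| 48 kg, 1.66 m | 48/1.66² = 17.4 | eligible | excluded | excluded | excluded |
| 70 kg, 1.75 m | 70/1.75² = 22.9 | eligible | eligible | eligible | eligible |

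**Step 6: a grid check.** The rules were run over 35 to 150 kg in 0.5 kg steps and 140 to 205 cm in 1 cm steps, which gives 231 × 66 = 15,246 points. Points excluded: literal 0, A 10,908, B 9,521, C 1,614. Everything B excludes, A excludes too, so A and B disagree at 10,908 − 9,521 = 1,387 points. The grid is an assumption and gives every body size equal weight. It confirms that the readings differ but does not estimate how many volunteers are affected.

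**The case against.** The strongest reply is that nobody will be misled. Two opposed BMI bounds in one exclusion are readily understood as an allowed range, and the likely intent is that any one limit excludes. Screening runs through one organisation's generic process, so different sites applying different rules is not an evident risk. Other criteria give a backstop: inclusion 3 on general health, exclusion 7 on venous access, and exclusion 16, "Any other finding that, in the opinion of the Investigator, deems the participant unsuitable for the study".

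Much of this stands. A reader might infer that the trial would in practice enrol people of any size. The documents do not support that, because they do not show staff applying the text literally. The backstops also soften the safety argument drawn from the blood volume. They do not restore the numeric limits, though, and they do not say whether a 48 kg volunteer with a BMI of 20.0 is eligible. The remaining ambiguity is narrow but real.

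A reader might also infer that a criterion 4 breach removes a participant from the efficacy analysis. The SAP does not say so. Under SAP 3.3.2.5 deviations are adjudicated before database lock and code break, and a major deviation may be classed as having potential impact on efficacy or not. SAP 3.1 leaves the final choice of participants to the Data Review Meeting. A breach can change the Evaluable set but need not, and the decision is made blind.

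**Conclusion.** The point holds as a drafting defect in an operative eligibility rule. As written, criterion 4 excludes nobody and nothing else in the documents supplies the limits. Once the BMI pair is repaired, the status of two groups still depends on the reading: weight ≤50 kg with BMI between 18 and 30, and BMI ≤18 with weight above 50 kg. This rests only on the wording and on BMI being a single value. The documents give no body-size distribution, so the number of volunteers affected is unknown. Sample size and power do not depend on it.

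Two stronger readings should be set aside.

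- A reader might infer that an affected participant would undermine the Part 1 dose decision, given only six participants. The documents do not show this. SAP 3.3.2.5 sits under Part 2, and the Part 1 PK set needs only one post-dose result (SAP 3.3.1.4), so an eligibility breach removes nobody from it. Nothing shows an effect on serum levels either.
- A reader might infer that every tall person with a low BMI changes status. That is not so: 48 kg at 1.70 m gives 48/1.70² = 16.6, which A and B both exclude. Weight must also be above 50 kg.

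**What to change.** Correct the connectives in exclusion 4 and leave the three limits as they are. The natural reading is that each limit excludes on its own, which means 'or' in both places. The documents do not confirm this, so the sponsor should state what was meant. Use the same wording when eligibility deviations are adjudicated for the Part 2 Evaluable set at the blind review under SAP 3.3.2.5.

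The cost is a change of wording with no new procedure or data. As a protocol amendment it needs IRB/IEC approval before it takes effect (Protocol 10.1.1), so it is best combined with any other amendment.
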